# EIRB Protocol Template (Version 1.7)

## 1.0 General Information

**\*Please enter the full title of your study:**

A pilot study of N-acetylcysteine for alcohol use disorder

**\*Please enter the Protocol Number you would like to use to reference the protocol:**

NAC

\* This field allows you to enter an abbreviated version of the Protocol Title to quickly identify this protocol.

**Is this a multi-site study (i.e. Each site has their own Principal Investigator)?**

No

**Does this protocol involve the use of animals?**

Yes  No

**3.4 If applicable, please select the Designated Site Approval(s):**

Add the name of the individual authorized to approve and sign off on this protocol from your Site (e.g. the Site Chair).

**4.0 Project Information**

**4.1 \* Has another IRB/HRPP reviewed this study or will another IRB/HRPP be reviewing this study? If Yes, answer the questions according to the IRB/HRPP Determination.**

Yes  No

**IRB Name**

**Review Date**

**Determination**

No records have been added

**4.2 \* Is this a research study or a Compassionate Use/Emergency Use/HUD project?**

Yes  No

**4.3 What type of research is this?**

- Biomedical Research
- Clinical trial (FDA regulated)
- Behavioral Research
- Educational Research
- Psychosocial Research
- Oral History
- Other

**4.4 Are you conducting this project in pursuit of a personal degree?**

Yes  No

**4.6 \* Is this human subjects research? (As defined by 32 CFR 219) Human subject means a living individual about whom an investigator (whether professional or student) conducting research:**

(i) Obtains information or biospecimens through intervention or interaction with the individual, and uses, studies, or analyzes the information or biospecimens; or  
(ii) Obtains, uses, studies, analyzes or generates identifiable private information or identifiable biospecimens.

Yes  No

**5.2 Will you have a Research Monitor for this study?**

Yes  
 No  
 N/A

**6.0**

## Data/Specimens

### 6.1 Does the study involve the use of existing data or specimens only (no interaction with human subjects)?

Yes  No

## 7.0

### Funding and Disclosures

#### 7.1 Source of Funding:

Funding Source	Funding Type	Amount
: Other	: Other	
USU	USU new faculty startup funds	150000

Total amount of funding:

150000

### 7.2 Do you or any other Investigator(s) have a disclosure of a personal interest or financial nature significant with sponsor(s), product(s), instrument(s) and/or company(ies) involved in this study?

Yes  No

If Yes, complete and attach Conflict of Interest forms for all key personnel

## 8.0

### Study Locations

#### 8.1 Is this a collaborative or multi-site study? (e.g., are there any other institutions involved?)

Yes  No

### 8.3 Are there international sites?

Attach international approval documents, if applicable, when prompted. Note: Ensure local research context has been considered

Yes  No

### 8.4 Is this an OCONUS (Outside Continental United States) study?

Yes  No

Select the area of responsibility:

Have you obtained permission from that area of responsibility? (This is a requirement prior to study approval)

Yes  No

## 9.0 Study Details

### 9.1 Key Words:

Provide up to 5 key words that identify the broad topic(s) of your study

NAC, n-acetylcysteine, AUD, alcohol use disorder

### 9.2 Background and Significance:

Include a literature review that describes in detail the rationale for conducting the study. Include descriptions of any preliminary studies and findings that led to the development of the protocol. The background section should clearly support the choice of study variables and explain the basis for the research questions and/or study hypotheses. This section establishes the relevance of the study and explains the applicability of its findings

Alcohol abuse is responsible for 1 in 10 deaths among working age adults in the U.S. and costs ~\$249 billion annually.(Stahre, Roeber, Kanny, Brewer, & Zhang, 2014) Currently approved medications for alcohol use disorder (AUD) exert only small to medium effects on drinking, with estimates indicating 12 to 20 drinkers need to be treated for one of them to benefit from the two leading medications, acamprosate and naltrexone.(Jonas et al., 2014) Thus, many patients do not benefit from current pharmacotherapies for AUD.

N-acetylcysteine (NAC) is one promising pharmacotherapy that is well-tolerated, safe, and exhibits preliminary evidence across a number of psychiatric and neurological disorders.(Minarini et al., 2017) NAC is available over the counter, has been used all over the world for a variety of conditions, most notably for its 1985 FDA approved use as an antidote for acetaminophen overdose.

The NAC dosage (3000 milligrams) was selected as most prior studies in addiction have used 2400-3000mg and even studies up to 3600mg have found it was well-tolerated (Minarini et al., 2017). Many studies using doses in this range achieved clinically significant improvements (e.g., Fernandes et al., 2016), including a study of NAC for smoking cessation which used 3000mg (Prado et al., 2015). 7 weeks was selected rather than 12 weeks or longer duration because this within the range of prior clinical trials of NAC (most are 8-12 weeks) and is fitting for the goals of this pilot trial seeking to establish feasibility and sample size for a larger clinical trial (Gray et al., 2010; Mardikian et al., 2007). It is beyond the primary aims of this study and the resources of the team to seek longer term outcomes (e.g., drinking at 6 months; <https://www.fda.gov/media/91222/download>).

**Neurobiological mechanisms.** NAC is an acetyl derivative of the amino acid cysteine, a precursor for the antioxidant glutathione.(Minarini et al., 2017) NACs purported utility for AUD comes from its downstream effects on neurotransmitters implicated in the development and maintenance of AUD: glutamate and dopamine. Alcohol abuse induces dysregulation of dopamine neurotransmission and enhancement of glutamatergic activity leading to alterations in reward, affect, and cognition.(Burnett, Chandler, & Tranham-Davidson, 2016) NAC enhances cystine to glutamate exchange via the  $x_c^-$  system that imports cystine inside glial cells and exports a glutamate molecule in the extracellular compartment. This may reverse addictive processes by reducing excitatory glutamatergic transmission and regulating dopamine release.(Dean, Giorlando, & Berk, 2011) Indeed, a recent rodent study found that NAC administered prior to chronic ethanol administration blocked three of the central processes: ethanol-induced behavioral sensitization (a method of studying drug-induced plasticity changes following repeated exposure(Legastelois, Botia, Coune, Jeanblanc, & Naassila, 2014)), an increase of  $\Delta$ FosB (accumulation of which increases the motivational properties of alcohol) in the prefrontal cortex, and a reduction of  $\Delta$ FosB in the nucleus accumbens.(Morais-Silva, Alves, & Marin, 2016)

**Basic preclinical research.** Findings demonstrate NAC crosses the blood-brain barrier and increases brain glutathione levels in rodents and in humans.(Reyes et al., 2016) A recent rodent investigation found that NAC reduced ethanol-reinforced responding in both a fixed and progressive ratio schedule, and it reduced reacquisition in rats abstinent for 17 days. (Lebourgues, González-Marín, Jeanblanc, Naassila, & Vilpoux, 2017) This is further supported by previous studies that found NAC decreased withdrawal-induced anxiety and elevated corticosterone levels(R Schneider, Santos, Clarimundo, & Dalmaz, 2015) as well as ethanol intake in a two-bottle choice paradigm.(Quintanilla et al., 2016) In the latter study, ethanol intake was only reduced following chronic administration (3 months), suggesting that NAC acts by counteracting neuroadaptations produced from chronic use. Indeed, it has been found to reduce alcohol-related neuroinflammation in rodents.(Ricardo Schneider et al., 2017)

**Human research.** A recent review details human studies on NAC for addiction.(Morley et al., 2018) Briefly, the two trials assessing the effect of NAC on alcohol use were secondary analyses in the context of cannabis trials. The first was a randomized, placebo-controlled trial in 277 adults with cannabis use disorder finding that NAC increased abstinence from alcohol and reduced drinking.(Squeglia et al., 2018) The second was a randomized, placebo-controlled trial in 116 cannabis using adolescents, finding reductions in drinking associated with changes in cannabis use.(Squeglia et al., 2016). Several studies on the effects of NAC on nicotine dependence have reported less nicotine craving, higher abstinence rates, and reduction in daily smoking (Gómez-Coronado, Walker, Berk, & Dodd, 2018).

With regard to clinical studies of NAC for other addictions, there have been three larger randomized controlled trials of NAC to date (Ns > 110). NAC reduced cannabis use in adolescents,(Gray et al., 2012) but had no effect in adults.(Gray et al., 2017) Furthermore, NAC reduced relapse in individuals with cocaine dependence, but only in the subset of patients that were initially abstinent.(LaRowe et al., 2013) Despite promising human studies, no prospective investigations to date have focused on NAC with alcohol use as the primary aim or on treatment-seeking drinkers.

**Potential mechanisms.** NAC may be particularly well-suited to treat some neuropsychiatric conditions that co-occur with drinking. Specifically, human and rodent studies identified beneficial effects of NAC on anxiety(Costa et al., 2017) and a meta-analysis found that NAC reduces depression and improves functionality.(Fernandes, Dean, Dodd, Malhi, & Berk, 2016) Given the influence of negative affect and stress on alcohol use,(Sinha et al., 2011) a reduction in these symptoms may also lead to better drinking outcomes.

Preliminary work has explored the effect of NAC on cognition. Preliminary findings suggest NAC may impact response inhibition(Schulte et al., 2018) and reduce cocaine attentional bias in individuals with cocaine use disorder.(Levi et al., 2017) Furthermore, NAC appears to improve cognition in individuals with schizophrenia.(Breier et al., 2018) Given the consistent association of a wide array of cognitive functions with AUDs,(Stavro, Pelletier, & Potvin, 2013) replication of these effects of NAC in individuals with AUDs may support potential mechanisms of its therapeutic effect.

### 9.3

#### Objectives/Specific Aims/Research Questions:

Describe the purpose and objective(s) of the study, specific aims, and/or research questions /hypotheses

The primary aim of the current study is to establish feasibility, dropout rate, and estimate the standard deviation of the outcome measures in order to estimate the required sample for a fully powered clinical trial and to refine the final measures for use in the fully powered clinical trial. The secondary aim is to explore preliminary efficacy signal of NAC. Specifically, we have primary, secondary, and tertiary hypotheses related to the putative effects of NAC: 1) NAC will reduce total drinking days and drinks per drinking day; 2) NAC will reduce alcohol cue-reactivity, alcohol demand on the alcohol purchase task (i.e., a measure assessing preferences for alcohol across a range of prices to determine the relative reinforcing value of alcohol), and trait-based craving; and 3) NAC will lead to improvements in response inhibition, working memory, processing speed, and executive functioning; and reductions in depression symptoms and anxiety symptoms. We will also explore change in total marijuana use days, total cigarette use days, and cigarettes per day in the subsets of individuals who use marijuana and cigarettes.

We anticipate this study will take 2 years to complete following approval (enrolling approximately 1 participant every other week).

#### **9.4 Study Design:**

Describe study design in one to two sentences (e.g., prospective, use of existing records/data /specimens, observational, cross-sectional, interventional, randomized, placebo-controlled, cohort, etc.). Specify the phase – Phase I, II, III, or IV – for FDA-regulated investigational drug research

Double-blind, randomized, placebo-controlled, pilot study

#### **9.5 Target Population:**

Describe the population to whom the study findings will be generalized

Adult Military Healthcare Beneficiaries enrolled in an outpatient AUD treatment program at a MTF.

#### **9.6 Benefit to the DoD:**

State how this study will impact or be of benefit to the Department of Defense

At-risk alcohol use increases risk for and impedes recovery from numerous conditions common to deployed military members including depression, posttraumatic stress disorder (PTSD), traumatic brain injury (TBI), and suicidality. Furthermore, it is associated with a myriad of health consequences including cancer, cardiovascular events, injuries, and violence. Military members drink even greater quantities of alcohol than their same-age peers in the general population, and high rates of binge drinking and at-risk use pose threats to overall troop readiness.

Many patients do not significantly benefit from current pharmacotherapies for AUD. NAC is one promising pharmacotherapy that is well-tolerated, safe, and exhibits preliminary evidence across a number of psychiatric and neurological disorders. This study will be an important step forward in determining if NAC is a potential treatment for AUD.

### **10.0**

#### **Study Procedures, Data Management, and Privacy**

##### **10.1 Study Procedures:**

Describe step-by-step how the study will be conducted from beginning to end

Individuals will be recruited from the Addiction Treatment Services center at WRNMMC. Specifically, the study team will post flyers on tables around ATS and will provide ATS staff with study flyers and a description of the research study. Preexisting patients as well as new patients will be informed of the study by ATS staff and provided a flyer. The ATS staff have agreed to mention the study both in individual and group settings (IOP). Study staff may also come to discuss the research study as requested by ATS. The study will typically be discussed with patients on the day of their intake. They will inform patients that it is a 7-week clinical trial of an experimental medication for AUD taking place at USU on base. It will not interrupt their current treatment and thus they can participate while in treatment at ATS. Given the exclusion criteria, focus will be on patients who have not opted to take an FDA approved medication for AUD. The ATS providers will wait to verbally inform patients about the study until after they have had an opportunity to be evaluated and recommended for FDA approved medication for AUD (e.g., naltrexone). Only those that are not taking FDA approved medications will be enrolled in the study. If they change their mind after enrolling in the study and want to take an FDA approved medication we will encourage them to discuss with their provider and follow their clinical recommendations. This will not impact their participation in the study and we will control for it statistically in our analysis.

Interested individuals will contact the research team and be screened over the phone for eligibility, then eligible participants will be scheduled for their baseline visit, ideally 1-3 weeks after the phone screen. Phone screening procedures are outlined in the table in 10.2. All in-person visits will take place at buildings 17 and 53 of the Uniformed Services University. 1-2 days prior to each scheduled appointment, participants will be called to confirm the appointment and screened for COVID symptoms. If any COVID symptoms are endorsed, they will be rescheduled and told to get tested for COVID and see their primary care provider (see NAC COVID screen and COVID screen phone call docs for additional details).

Below are brief descriptions of the procedures for each study session (for a detailed description of the study protocol and assessments see "NAC script" and "NAC assessments" attachments, respectively):

#### Baseline Visit (Wk 0)

Participants will be temperature checked with a non-contact thermometer and screened for COVID symptoms. If their temperature is 100.4°F and above or they endorse any of the COVID symptoms, they will be rescheduled and told to get tested for COVID and see their primary care provider. Participants will be administered a breathalyzer by the research assistant (RA) to check BAC. If BAC is > 0, the RA will wait a few minutes and readminister. If BAC is 0, the RA will proceed with the study. If BAC is between .01 and .049, the RA will have the participant wait until it drops to 0. If the participant refuses to wait, the research team will reschedule their appointment and the participant can leave. If BAC is  $\geq .05$ , the participant will be transported to the WRNMMC emergency department to assess alcohol withdrawal. If the participant refuses to go to the emergency department, they will be informed that the research team will be forced to contact the NSA Bethesda police ([contact]) out of concern for their safety. A member of the study team will walk the participants unless by the judgement of the research assistant, the participant is unable to walk unassisted. In this case, we will contact 911 to dispatch a team to evaluate the participant and transport them as needed to the WRNMMC ED.

Participants with a BAC of 0 will complete the informed consent process. They will undergo a physical exam by the physician. During the physical, female participants will undergo a pregnancy screen using a pregnancy test kit. If the screen is positive, they will be told they are not eligible to participate and they will not be counted in the study's enrollment number. Further, they will be instructed to contact their primary care provider to confirm the results and discuss the risks of alcohol use during pregnancy. Next, the RA will conduct the MADRS interview, then participants will complete the TLFB self-report form. They will then complete the computer questionnaires (demographics, ASSIST, AUDIT, APT, PACS, DDT, SIAS-6, SPS-6, e-cigarette questions, HONC, GAD-7, mental health services, medications and supplements, and military service questions) and behavioral tasks (Stop Signal, N-back, and Trail Making). Participants will be asked the treatment questions and referred to mental health resources by the RA. They will then be scheduled for their next study session and complete payment paperwork with the RA. Then they will be randomized to either 7 weeks of oral NAC (3000 milligrams) or 7 weeks of placebo. We will advise participants to inform their provider of participating in this research study and of taking 3000mg NAC or placebo. Participants will be given a business card to give to their provider stating they are in the study and taking 3000mg of NAC or placebo. Participants will be instructed to go to the Investigational Pharmacy (building 9) immediately after their appointment to pick up their study medication. They will be escorted by the RA if they have never been before or don't remember how to get there. The pharmacy will handle gender stratified randomization. The first study session will take approximately 3 hrs to complete.

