#### 13.3 Please describe the pre-screening process. If no pre-screening, enter Not Applicable in the text editor

Participants will complete a brief phone screen in which they will be asked the following eligibility criteria questions:

1. *Have you used any drugs other than marijuana in the past 30 days?*  
*If yes: Which drugs?*
2. *Have you ever had a seizure?*
3. *Have you ever had delirium tremens or DT?*
4. *Have you been to the hospital because of alcohol use in the past 12 months?*
5. *Have you ever been diagnosed with schizophrenia?*
6. *Have you ever been diagnosed with bipolar disorder?*
7. *Have you ever been diagnosed with a neurocognitive disorder such as dementia or Alzheimer's?*
8. *Have you ever been diagnosed with an intellectual disability such as mental retardation? (NOTE: ADHD is ok)*
9. *Do you have any chronic medical conditions associated with alcohol use (such as liver disease)?*
10. *Are you currently receiving medication for the treatment of alcohol use disorder? If so, what medication are you taking? [Exclude if taking oral or injectable naltrexone (ReVia, Vivitrol), disulfiram (Antabuse), and acamprosate (Campral)]*
11. *Female only: Are you pregnant or trying to get pregnant sometime in the next 4 months?*
12. *How old are you?*

SCID-5 AUD module

If they meet eligibility criteria, they will be scheduled for their baseline visit. They will be told that they need to be abstinent from alcohol for at least 24 hours before their baseline appointment and that they will be breathalyzed to confirm a BAC of 0.

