#### 13.4 Consent Process: Revised Common Rule, Section 219.116: General requirements for informed consent, whether written or oral, are set forth in this paragraph and apply to consent obtained in accordance with the requirements set forth in paragraphs (b) through (d) of this section. Broad consent may be obtained in lieu of informed consent obtained in accordance with paragraphs (b) and (c) of this section only with respect to the storage, maintenance, and secondary research uses of identifiable private information and identifiable biospecimens.

Are you requesting a waiver or alteration of informed consent?

Yes  No

Please explain the consent process:

Participants will complete the consent process at the baseline visit in a private room at USU Building 53. Participants will be instructed to read the consent form and ask any questions before signing, then sign. A copy of the consent form with participant and research team signatures will be provided to participant following the consent process.

**13.5 DoDI 3216.02 requires an ombudsman to be present during recruitment briefings when research involves greater than minimal risk and recruitment of Service members occurs in a group setting. If applicable, you may nominate an individual to serve as the ombudsman.**

N/A  
 Propose ombudsman

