**14.0 Risks and Benefits**

**14.1 Risks of Harm:**

Identify all research-related risks of harm to which the subject will be exposed for each research procedure or intervention as a result of participation in this study. Consider the risks of breach of confidentiality, psychological, legal, social, and economic risks as well as physical risks. Do not describe risks from standard care procedures; only describe risks from procedures done for research purposes

Side effects of NAC are uncommon and relatively minor. The most frequently reported side effects are nausea, vomiting, and diarrhea. They often occur at identical rates to placebo. Rarely and primarily with intravenous administration, anaphylactic reactions may occur and can consist of rash, pruritus, angioedema, bronchospasm, tachycardia, and blood pressure dysregulation. Finally, given the limited reports on NAC in pregnant and lactating women, it should not be used in this population in the context of research and thus this is an exclusion criteria.

Sources: 1) FDA approved acetylcysteine labels (<https://dailymed.nlm.nih.gov/dailymed/index.cfm>)

Data collection may risk loss of privacy.

There is a risk of alcohol withdrawal.

There are legal risks if the participant enters the base intoxicated and/or the NSAB police are called.

There is a chance that participants could experience side effects such as nausea, motion sickness, eye strain, or seizures while completing the virtual reality-based assessment. Symptoms of virtual reality exposure can persist and become more apparent hours after use. These symptoms may put participants at an increased risk of injury when engaging in normal activities such as driving, operating machinery, or engaging in other demanding activities.

For military personnel, there is a risk that their command could be informed of their intoxication by the emergency department if the participant is transported there for alcohol withdrawal.

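### At baseline, the 24-hour abstinence instruction and the emergency-department/police step come before consent and the study physician's exam, and no withdrawal check is named for people who arrive at zero BAC

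*Combined protocol and SAP*

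**What the plan says.** **Phone screen (13.3).** Eligible people are booked for baseline. "They will be told that they need to be abstinent from alcohol for at least 24 hours before their baseline appointment", and that a breath test will confirm a BAC of 0.

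**Interval and reminder call (10.1).** Baseline is ideally 1 to 3 weeks after the screen. One to two days before each appointment, "participants will be called to confirm the appointment and screened for COVID symptoms". No other content is stated for that call.

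**Arrival (10.1, Baseline Visit).** The research assistant breathalyzes. At .01 to .049 the person waits for zero, or is rescheduled and may go. At .05 or more, "the participant will be transported to the WRNMMC emergency department to assess alcohol withdrawal". On refusal, "they will be informed that the research team will be forced to contact the NSA Bethesda police". Section 14.6 describes the same step less firmly, as something that may be needed.

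**Consent, then exam (10.1, 13.4).** "Participants with a BAC of 0 will complete the informed consent process". Next: "They will undergo a physical exam by the physician". Section 13.4 agrees on the timing: "Participants will complete the consent process at the baseline visit in a private room at USU Building 53". The schedule in 10.2 also marks both at baseline.

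**Risks (14.1, 14.2).** Section 14.1 states: "There is a risk of alcohol withdrawal". It also lists legal exposure if someone comes onto the base intoxicated or police are called and, for military personnel, the chance that the emergency department informs their command. Section 14.2 covers concurrent alcohol medications, side effects, virtual reality and confidentiality.

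**The concern.** A person who is still drinking is asked by the study to stop for a day before the consent process has explained withdrawal and before the study physician has seen them. Separately, a person who arrives at .05 or more can be sent to the emergency department or reported to police without having agreed to take part. A service member in that position may also become known to command. Active-duty personnel are expected participants, since 13.2 sets a payment rule for them.

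The template for 14.1 asks for research-related risks and excludes those of standard care. By listing these three risks there, the sponsor treats them as consequences of the study. The consent form and the baseline exam cannot protect against events that precede both.

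**Working it through.** No formula applies and the plan gives no figure to reproduce. The check sets the steps in order and then looks for every place where withdrawal is assessed.

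**Order at baseline**

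| Step | Where stated | Before consent? | Before study physician's exam? |
|---|---|---|---|
| 24-hour abstinence instruction, by phone | 13.3 | Yes | Yes |
| Reminder call, 1–2 days before | 10.1 | Yes | Yes |
| The abstinence day itself | 13.3 | Yes | Yes |
| Breath test on arrival | 10.1 | Yes | Yes |
| Emergency department at BAC .05 or more; police if refused | 10.1, 14.6 | Yes | Yes |
| Written consent, at BAC 0 only | 10.1, 13.4, 10.2 schedule | – | Yes |
| Physician's exam | 10.1, 10.2 schedule | No | – |
| Randomization | 10.1 | No | No |

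By this order, everyone who enters the emergency-department branch at baseline is unconsented.

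**Where withdrawal is assessed.** Each mention is the same BAC-triggered step: 10.1 at baseline, at weeks 1, 3 and 5 and at week 7, and again in 14.6. The content of the physician's exam is not described in 10.1 or 10.2 beyond the pregnancy screen. The adverse-event items in 16.1 include symptoms such as nausea, anxiety and insomnia but none for withdrawal, and 10.1 describes that interview from week 1 onward.

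**Two groups, two gaps.**

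- *Those who comply and arrive at BAC 0* have been through the abstinence day. The trigger does not fire for them, so no withdrawal assessment is specified.
- *Those who arrive at .05 or more* meet the trigger, but before any stated explanation of the emergency-department, police and command consequences.

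**Reach.** The instruction goes to all 50 planned participants (11.2) and to anyone booked who does not enroll. It carries withdrawal risk only for those still drinking. Neither their number nor the number expected at .05 or more is given. The ordering problem affects 1 of 5 in-person visits (baseline plus weeks 1, 3, 5 and 7); at the other four, consent has been given.

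**The case against.** The case on the other side has substance.

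- **Consent must wait for BAC 0.** This is correct on capacity grounds, and nothing here argues for moving written consent earlier. It leaves open what is disclosed by phone, when the instruction is given.
- **The emergency-department step is protective.** It is a safety response to someone intoxicated on a military base, and 14.6 words it more softly. It should stay. The question is whether people know of it beforehand.
- **Exclusions 6 and 7 screen for risk.** Alcohol-related hospitalization in the past 12 months and any history of seizures or delirium tremens are asked about by phone. This lowers risk, but it is history and not a check on current drinking or withdrawal.
- **People come from a treatment clinic.** Those never enrolled in Addiction Treatment Services are excluded (12.6), and clinic providers are to raise the study verbally only after patients could be evaluated for approved medication (10.1). A reader might infer that no clinician has been involved before the abstinence day. The text supports only that the *study* physician has not. Since 12.5 does not require current treatment, the protection is partial.
- **Adverse-event follow-up exists.** A reader might infer that milder withdrawal has no route to care. The Clinical Follow-up Plan in 16.1 says otherwise: any event judged to need management goes to primary care, moderate events are followed, and serious events that warrant it go to the emergency department.
- **The calling text is not available.** Section 10.1 refers to a NAC script that was not supplied, and the waiver tick in 13.4 cannot be read. The documents therefore do not show that people are told nothing; they show only that 13.3 and 13.4 describe no such disclosure beyond the breath test and the BAC 0 requirement.

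**Conclusion.** The order holds on the supplied text. The abstinence instruction and the emergency-department/police step precede both consent and the study physician's exam. A person who complies and arrives at zero has no named withdrawal check, and 14.2 offers no measure for three risks that 14.1 lists. Relevant measures do sit elsewhere (10.1, 12.6, 14.6, 16.1), so part of the 14.2 gap is missing cross-reference.

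This is a participant-safety and consent point that merits a change because the remedy is small. It does not touch randomization, outcomes or sample size.

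Its size cannot be given in numbers. One could assume a share of arrivals at .05 or more and compute the chance of at least one such event among 50, but the result would reflect only the assumption, and it would count breath-test readings and not harms. The conclusion assumes that the protocol text is followed as written and that the unsupplied NAC script contains no fuller disclosure. If it does, the phone-disclosure part reduces to stating it in 13.3 and 13.4.

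**What to change.** 1. **Phone disclosure (13.3, 13.4).** Before the abstinence instruction, have the caller explain the withdrawal risk, the breath test, the emergency-department and police rule, and possible command notification. Record verbal agreement to these pre-visit steps and describe this in 13.4 for IRB approval. Keep written consent at BAC 0.
2. **Reminder call (10.1).** Ask about current drinking and past withdrawal symptoms. If the answers raise concern, the study physician decides whether the abstinence and the visit go ahead. Make the call nearer two days than one day before the visit, because at one day the 24-hour period is already due to begin.

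Two wording changes could ride on the same amendment: state in 10.1 that the physician's exam looks for withdrawal signs before randomization, and in 14.2 cite the exclusions, the BAC procedure and the exam. They tidy the text but do not alter the order, since the exam follows the abstinence day.

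**Cost.** A few minutes per call, occasional physician time and an IRB amendment, with no added visit. Some people may decline or be rescheduled, which could slow the planned pace of about one enrollment every two weeks (9.3).
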